4.12 Description of post investigational provision of medical care

When the subject's participation in the clinical investigation has been completed (prematurely) or terminated, the subject will return to the medical care as per physician's recommendation.

5 Clinical Investigation Conduct

5.1 Ethics Committee

A duly constituted EC representing the prospective study site must review and approve the subject informed consent, the clinical investigation plan, the prospective investigator's participation in the study, and any other study related information to be provided to the subjects

prior to subject enrollment. Additionally, the Investigator must be aware of and adhere to all EC requirements such as, but not limited to: the submission of progress reports, serious adverse events, and protocol deviations.

EC approval record should clearly identify:

- the date of the meeting
- constitution of the committee and voting members present at the meeting
- the approved version of the Clinical Investigation Plan
- the approved version of the Patient Information Sheet and Patient Informed Consent
- the approved version of the Instructions for Use (IFU)

Approval from the EC is necessary prior to the start of the investigation. The original approval is to be filed in the Investigator Study Binder and a copy of the approval is provided to SJM prior to commencing study activities.

Any amendments to the protocol should be submitted to the relevant EC. The EC will be informed about SAEs and UADEs in accordance with local and national requirements.

5.2 Ethical Basis

This clinical investigation will be performed in accordance with the World Medical Association Declaration of Helsinki (Appendix F) and applicable local and national legal and regulatory requirements. Prior to starting the investigation, the Clinical Investigation Plan will be submitted together with associated documents including Patient Information Sheets, and subject Informed Consent Forms in the local language to the relevant EC for review.

5.3 Insurance

St. Jude Medical, as the Sponsor, has taken out insurance for all subjects participating in this study in accordance with the requirements of the local laws.

5.4 Statements of Compliance

The investigation will be performed in accordance with the most current versions of the World Medical Association (WMA) Declaration of Helsinki and any regional and/or national regulations, as appropriate.

The investigator shall not start enrolling subjects or requesting informed consent prior to obtaining Ethics Committee approval and authorization from the sponsor in writing for the investigation.

In case additional requirements are imposed by the Ethics Committee, they shall be followed, if appropriate.

As sponsor, SJM will maintain insurance for this investigation in accordance with the requirements of the applicable local laws.

5.5 Adherence to the Clinical Investigation Plan

The Principal Investigator and delegates are required to adhere to the CIP in order to prevent subjects being exposed to unreasonable risks. The Principal Investigator and delegates are also required to be compliant with the signed Study Agreement, applicable national or local laws and regulations, and any conditions required by the appropriate EC or applicable regulatory authorities. Instances of failure, intentionally or unintentionally, to adhere to the requirements of the CIP are considered a deviation and corrective action(s) may be taken to prevent these instances from occurring again.

In some cases failure to comply with the CIP may be considered failure to protect the rights, safety and well-being of subjects, since the non-compliance potentially exposes subjects to unreasonable risks. For example, failure to adhere to the inclusion/exclusion criteria: these criteria are specifically defined by the Sponsor to exclude subjects for whom the device is not beneficial and the use involves unreasonable risks. This may be considered failure to protect the rights, safety and well-being of the enrolled subject. Similarly, failure to perform safety assessments intended to detect adverse events may be considered failure to protect the rights, safety and well-being of the enrolled subject. Investigators should minimize such risks by adhering to the CIP.

Simultaneously, in the event that adhering to the CIP might expose the subject to unreasonable risks, the investigator is also required to protect the rights, safety and well-being of the subject by intentionally deviating from the requirements of the CIP, so that subjects are not exposed to unreasonable risks. It is the responsibility of the investigator to provide adequate medical care to a subject enrolled in an investigation.

The PI shall promptly report any deviations from the CIP to the Sponsor that affect the rights, safety or well-being of the subject or the scientific integrity of the clinical investigation, including those which occur under emergency circumstances. The reporting of these deviations should be done as soon as possible but no later than 72 hours after the investigator becomes aware. The investigator shall also promptly notify the EC per their requirements.

Any corrective and preventive actions required by the EC must be complied with by the site.

The Sponsor will notify the EC as per their requirements.

5.5.1 Repeated non-compliance

In the event of repeated non-compliance, as determined by the Sponsor, a Clinical Research Associate or sponsor representative will attempt to secure compliance by one or more of the following actions:

- Visiting the investigator
- Contacting the investigator by telephone
- Contacting the investigator in writing
- Retraining of the investigator

If an investigator is found to be repeatedly non-compliant with the signed agreement, the CIP or any other conditions of the clinical investigation, the Sponsor will either secure compliance or, at its sole discretion, terminate the investigator's participation in the clinical investigation.

5.6 Informed Consent Process

5.6.1 General Process

Provision of the Informed Consent is mandatory. Informed Consent is required from all patients prior to participation in the investigation. The process of obtaining Informed Consent shall comply with the most recent version of the Declaration of Helsinki, ISO 14155:2011 and all applicable regulations.

The Principal Investigator or his/her authorized designee will conduct the Informed Consent Process. This process will include a verbal discussion with the patient on all aspects of the clinical investigation that are relevant to the patient's decision to participate in the clinical investigation. It is crucial that this discussion is documented in the source documents (hospital records).

Prior to enrolling in the clinical study, patients shall be fully informed of the details of clinical study participation as required by applicable regulations and the study center's EC, and/or Head of Medical Institution. Informed consent must be obtained from each patient prior to any clinical study participation using the Patient Information Sheet (PIS) and Patient Informed Consent form (PIC) approved by both the Sponsor, and the study center's EC,. Prior to the patient signing the PIS, the investigator or authorized delegate will fully explain to the patient the nature of the research, clinical study procedures, anticipated benefits, and potential risks of participation in the clinical study.

The patient will be provided with the EC approved patient information sheet and informed consent form that is written in a language that is understandable to them (native non technical language) and sufficient time is provided to the patient to consider participation and ask questions if necessary. The study site personnel will provide answers to the patient's questions.

If a patient is unable to read or write, the consenting shall be obtained through a supervised oral process. An independent witness shall be present throughout the process. The consent form must be signed and dated by the patient and by the person obtaining the consent attesting that the information was accurately explained and that informed consent was freely given.

If the patient does not sign and date the PIC, he/she cannot participate in the investigation, and no further CIP required activities are allowed. If the patient has provided written informed consent, signature and date from the Principal Investigator or authorized designee will be obtained on the EC approved informed consent form.

In order to avoid any possible coercion or undue improper influence on, or inducement of the patient to participate, the Sponsor requests the investigator to only sign the informed consent form once the subject has signed and dated the document and therefore decided to participate in the investigation.

Informed Consent of a subject shall always be indicated by personally dated signature of the subject and by the investigator responsible for conducting the Informed Consent process.

The original signed consent document must be retained on file by the investigator and a copy of the signed consent document is provided to the subject (investigator's responsibility).

The subject's legal rights will not be waived, nor will it appear that these will be waived.

Important new information that becomes available throughout the clinical investigation will have to be provided in writing to new and existing subjects. If relevant, all affected subjects will be provided a new consent form to review and re-sign, should they decide to maintain participation in the investigation.

5.7 Adverse Event, Adverse Device Effect

Definitions

The definitions provided below are in accordance to ISO 14155:2011 (E).

5.7.1 Medical device

Any instrument, apparatus, implement, machine, appliance, implant, software, material or other similar or related article.

- Intended by the manufacturer to be used, alone or in combination, for human beings for one
 or more of the specific purpose(s) of
 - Diagnosis, prevention, monitoring, treatments or alleviation of disease,
 - Diagnosis, monitoring, treatment, alleviation of, or compensation for, an injury,
 - Investigation, replacement, modification, or support of the anatomy or of a physiological process,
 - Supporting or sustaining life,
 - Control of conception.
 - Disinfection of medical devices and
- Which does not achieve its primary intended action in or on the human body by pharmacological, immunological or metabolic means, but which may be assisted in its intended function by such means

5.7.2 Adverse Event (AE)

Any untoward medical occurrence, unintended disease or injury, or untoward clinical signs (including abnormal laboratory findings) in subjects, users or other persons, whether or not related to the medical device.

Note: This definition includes events related to the medical device or the comparator.

Note: This definition includes events related to the procedures involved.

5.7.3 Serious Adverse Event (SAE)

An adverse event that led to:

Death

Clinical Investigational Plan: RDN + AF

- A serious deterioration in the health of the subject, that either resulted in:
 - A life-threatening illness or injury OR
 - o A permanent impairment to a body structure or a body function OR
 - An in-patient or prolonged hospitalization OR
 - A medical or surgical intervention to prevent life-threatening illness or injury or permanent impairment to a body structure or a body OR
 - o A malignant tumor
- Fetal distress, fetal death or a congenital abnormality or birth defect

Note: A planned hospitalization for a pre-existing condition, or a procedure required by the CIP, without serious deterioration in health, is not considered a serious adverse event.

5.7.4 Adverse Device Effect (ADE)

An adverse event related to the use of an investigational device.

Note: This definition includes adverse events resulting from insufficient or inadequate instructions for use, deployment, implantation, installation, or operation, or any malfunction of the medical device.

Note: This definition includes any event resulting from the use error or from intentional misuse of the medical device.

5.7.5 Serious Adverse Device Effect (SADE)

Adverse device effect that has resulted in any of the consequences characteristic of a serious adverse event.

5.7.6 Unanticipated Serious Adverse Device Effect (USADE)

A serious adverse device effect which by its nature, incidence, severity or outcome has not been identified in the current version of the risk analysis report.

5.7.7 Anticipated Serious Adverse Device Effect (ASADE)

A serious adverse device effect which by its nature, incidence, severity or outcome has been previously identified in the risk analysis report.

5.7.8 Procedure for assessing, recording and reporting adverse events, adverse device effects, serious adverse events and serious adverse device effects:

Safety surveillance and reporting will be done for all subjects enrolled in this investigation as described below.

Safety surveillance within this investigation and the safety reporting performed by the investigator, starts as soon as the subject is enrolled in this investigation (date of signature of the informed consent). The safety surveillance and the safety reporting will continue until the last

investigational visit has been performed or the subject is deceased or the subject/investigator concludes his participation into the investigation.

For the purpose of this trial, all Serious Adverse Events and all Adverse Device Effects (regardless of severity) are to be documented and reported to the sponsor immediately and this no later than 72 hours after becoming aware of the event.

Adverse events will be assessed by the investigator for relationship to the device and to the procedures involved.

- Procedure related: The AE is deemed related to the procedure if it occurred during the procedure but was not directly caused by the medical device.
- Device related: The AE is deemed device related if it was directly caused by the medical device.

Investigators are responsible for promptly reporting all SAEs and ADEs to the sponsor by completing the Adverse Event form. All unresolved AEs should be followed by the investigator until resolution is reached.

Note: Refer to Table 1 'Data Collection' and Appendix G 'Data Collection Method'. In case of EDC failure, notify Sponsor via Fax ([contact]) or via [contact].

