7.3 Analysis Population

All patients who have signed a Patient Informed Consent (PIC) will be considered enrolled in the study. However, the Primary Analysis population will only include those patients that have signed a PIC, have undergone a cardiac ablation procedure for the treatment of atrial fibrillation, and, if in the renal denervation arm of the study, had the EnligHTN™ Renal Denervation System enter his/her body.

It is anticipated that there may be subjects who have been enrolled in the study but are not included in the Primary Analysis population, such as:

- Subjects who are enrolled but do not meet baseline inclusion or exclusion criteria before the procedure; these are considered the screen failure population.
- Procedurally excluded populations will include subjects who have enrolled in the study and start the procedure, but do not undergo a cardiac ablation procedure for the treatment of atrial fibrillation or if in the renal denervation arm of the study and do not have the EnligHTN™ Renal Denervation System enter his/her body, due to their anatomy, circumstances related to the procedure, or physician judgment.

Subjects who withdraw from the investigation will not be replaced in any analysis population.

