#### 1.3 Definitions

Role/Term	Definition
SJM Clinical Team	Those individuals working within the GCAO clinical affairs department at the
(SJMCT)	project manager level or lower (e.g. Clinical Project Manager, CRAs, CRCs,
	etc.)
Field Clinical	Those individuals providing EnligHTN procedure training, case coverage,
Engineers (FCE)	and other administrative support. For the purposes of this document, this
	refers to FCE Directors, FCE Managers, and all other levels of FCEs that have been assigned to work on the RD+AF trial.
Monitor	This is a subset of the SJM personnel or CRO personnel who have received
	monitoring training outside of this plan. They are responsible for oversight
	of specific study sites and will be performing on-site monitoring visits. They
	may or may not be part of the SJMCT.
Site Personnel (Site)	Those individuals working as part of the RD+AF trial as an employee or agent of the study site.
Data Management	Those individuals working within the Data Management group at SJM in the
Personnel (DM)	GCAO (e.g. database developers and report programmers)
Vendor (V)	Any non-study site entity outside of SJM that has been contracted to
	perform services or provide equipment for study execution.
Statistics (Stats)	Those individuals within the Biostatistics group at SJM in the GCAO that are
	involved with the trial.
Safety Personnel	Those individuals within the Clinical Safety group of the GCAO at SJM that
(Safety)	are involved with analysis and reporting of adverse events.
Regulatory (Reg)	Those individuals within the Regulatory Affairs group at SJM in CATD that
	are involved with the trial.
Trial Master File (TMF)	Electronic files kept in Windchill

For any other terms, please consult the RD+AF clinical investigation plan (#SJM-CIP-0009).

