#### 2.5 The Secondary objectives

#### 2.5.1 Safety Acute data

The major adverse cardiac events (MACE) within 7 days post procedure will be summarized as a percentage of patients as defined as:

Number of subjects with major adverse cardiac events within 7 days post procedure Number of subjects with at least 7 days of follow – up or who experienced an event \* 100

The denominator includes subjects who either had an event within 7 days post procedure or were eligible to meet the endpoint, i.e. followed through at least 7 days.

The peri-procedural events will be summarized as a percentage of patients as described below. Rates will be calculated for each randomization arm.

Number of subjects with at least one event within 30 days post procedure Number of subjects with at least 30 days of follow – up or who experienced an event \* 100

All serious and possibly device or procedure related adverse events are reported and adjudicated by an internal medical expert. An event is considered a MACE if it meets the criteria defined in the Adverse Event Adjudication Plan.

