#### 2.5.2 Safety Midterm (6 months) and Long term (1-2 years) data

For all patients, the major adverse cardiac events will be recorded and summarized at 6 months, 1 year, and 2 years. Event rates will be calculated for each arm as the number of subjects who experienced a major adverse cardiac event over the number of subjects who experienced an event within or were followed to each time interval. Kaplan-Meier analysis may be performed for time to first major adverse cardiac event. For patients undergoing the renal denervation procedure:

The new (or worsened) renal artery stenosis (>50%) and/or aneurysm at the site of

- ablation per Renal Artery Imaging will be summarized at 6 and 12 months. A percentage of patients who have new stenosis and/or aneurysm compared to baseline will be provided. The denominator includes subjects with a baseline and follow-up assessment at the corresponding interval. Image interpretation will be based on local analysis. Kaplan-Meier analysis may be performed if applicable on the time to the first new renal artery stenosis and/or aneurysm at the site of ablation.
- Renal function change based on eGFR will be summarized by computing the change of the eGFR at 6 months, 12 months and 2 years compared to baseline (follow-up interval baseline) for each patient with data available in both time points. The mean and standard deviation of the eGFR change at those intervals will be presented.
- Overall renal vascular safety will be summarized as a rate of subjects with a serious, device or procedure related event over total subjects randomized to the renal denervation group at each follow-up time point.

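### The timing-based rule for procedure relatedness can leave a late procedure-caused event out of the SAP's overall renal vascular safety rate, and the rate's denominator is not clearly stated

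*Protocol*

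**What the plan says.** **Relatedness.** Protocol 5.7.8 gives the investigator two labels. For the procedure: "The AE is deemed related to the procedure if it occurred during the procedure but was not directly caused by the medical device". For the device, the test is direct causation by the device. Protocol 5.7.4 defines an adverse device effect more broadly: "An adverse event related to the use of an investigational device". Its notes bring in inadequate instructions, malfunction and use error. It sets no time limit and does not require direct causation.

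**The rate.** The last bullet of SAP 2.5.2 gives an overall renal vascular safety rate, whose numerator and denominator are set by these words: "serious, device or procedure related event over total subjects randomized to the renal denervation group at each follow-up time point". The SAP does not define relatedness. SAP 1.3 says: "For any other terms, please consult the RD+AF clinical investigation plan".

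**The denominator.** That bullet stands under the lead-in "For patients undergoing the renal denervation procedure". In the same section, MACE is calculated per arm "over the number of subjects who experienced an event within or were followed to each time interval". SAP 2.3 makes the Primary Analysis population the default unless otherwise specified. In the renal denervation (RDN) arm that population requires the device to have entered the body (SAP 2.2). Both documents foresee RDN-arm subjects in whom it did not (Protocol 3.8 and 7.3, SAP 2.2).

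**Review of events.** SAP 2.5.1 adds: "All serious and possibly device or procedure related adverse events are reported and adjudicated by an internal medical expert". Protocol 12.1 has the sponsor review the investigator's assessments and document seriousness and relationship to the device.

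**The concern.** Relatedness decides which serious events enter this rate. The 5.7.8 rule for procedure relatedness asks when an event happened, not what caused it. A complication that the procedure set in motion but that shows itself after the patient leaves the table fails that test. If it is also not judged directly caused by the device, it fails the other test too. The same event could still be an adverse device effect under 5.7.4, so the protocol offers two breadths for one idea.

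The denominator raises a separate question. The lead-in points to treated patients, the bullet names randomised patients, and the neighbouring MACE rate uses a third rule. Two analysts could compute different rates from the same data, and the 6-, 12- and 24-month renal figures might not be on the same basis as the MACE figures beside them.

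At stake is one descriptive safety summary for the study device. The primary analysis, the sample size and error control are untouched, since the study plans no hypothesis test.

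**Working it through.** The documents state no value for this rate, so there is none to reproduce. The one related figure checks: 2/3 × 75 = 50, the SAP's minimum for the RDN group (SAP 2.2).

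**Numerator: four kinds of serious renal vascular event against the two definitions**

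| Event | 5.7.8 label | In the SAP rate? | ADE under 5.7.4? |
|---|---|---|---|
| Directly caused by the device, any time | Device related | Yes | Yes |
| Caused by the procedure, occurs during it, not directly by the device | Procedure related | Yes | If related to device use |
| Caused by the procedure, appears later, not judged directly device-caused | Neither | No | If related to device use |
| Incidental, happens to occur during the procedure | Procedure related | Yes | No |

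The third row is the gap. How many events fall there cannot be derived from the documents. As a scale only, assume 3 true events:

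- 50 subjects: 3/50 = 6.0%. If one event is left out, 2/50 = 4.0% (exact 95% CI 0.49 to 13.71), which is 2.0 points lower.
- 67 subjects (2/3 of the protocol's 100 = 66.7): 3/67 = 4.5%. If one event is left out, 2/67 = 3.0%, which is 1.5 points lower.

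**Denominator**

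Inputs: at least 50 treated (SAP 2.2, Protocol 3.11). Procedurally excluded subjects do not count towards that number (Protocol 3.11), so untreated subjects come on top of it. Assumptions, not document figures: 3 subjects with events, all treated; u = 0 or 5 randomised but untreated; d = 0, 5 or 10 treated subjects who leave event-free before the time point.

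All randomised: 3/(50 + u). Event or followed: 3/(50 − d).

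| u | d | All randomised | Event or followed | Gap (points) |
|---|---|---|---|---|
| 0 | 0 | 3/50 = 6.0% | 3/50 = 6.0% | 0 |
| 5 | 0 | 3/55 = 5.5% | 3/50 = 6.0% | 0.5 |
| 0 | 5 | 3/50 = 6.0% | 3/45 = 6.7% | 0.7 |
| 5 | 5 | 3/55 = 5.5% | 3/45 = 6.7% | 1.2 |
| 0 | 10 | 3/50 = 6.0% | 3/40 = 7.5% | 1.5 |
| 5 | 10 | 3/55 = 5.5% | 3/40 = 7.5% | 2.0 |

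Exact (Clopper-Pearson) 95% intervals: 3/55, 1.14 to 15.12; 3/50, 1.25 to 16.55; 3/45, 1.40 to 18.27; 3/40, 1.57 to 20.39. They overlap almost completely.

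**The other reading.** If the SAP 2.3 default applies, u drops out of the denominator. If the closing words of the bullet, about each follow-up time point, mean subjects still present then, d drops out as well. The rate then comes close to the event-or-followed figure and the gap is near zero. With the default population alone, only the effect of d remains: 6.0% against 6.7% when d = 5.

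**The case against.** **The 5.7.8 label may not be what enters the rate.** The sponsor reviews relationship to the device (Protocol 12.1), and an internal expert adjudicates serious and possibly related events (SAP 2.5.1). This stands in part. But the sponsor's duty names the device, not the procedure, and the only criteria SAP 2.5.1 takes from the Adverse Event Adjudication Plan are those for MACE. That plan is not among the documents and may be broader. Nothing provided states a relatedness rule that overrides 5.7.8.

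**The missed set is very small.** This stands. The event must be renal vascular, serious, procedure-caused, late, not attributed to the device and uncorrected on review. Most renal vascular injuries would ordinarily be put down to device use. Access-site complications are a tempting example, but Protocol section 6 lists them apart from renal vascular injury, so they may not belong in this rate.

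**Three stronger readings should be resisted.**

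- A reader might infer that late events are lost to safety reporting. They are not: Protocol 5.7.8 requires all serious adverse events to be reported whatever their relatedness. New stenosis or aneurysm on imaging, MACE and the 30-day rate are also summarised separately, without this timing limit.
- A reader might infer that the rule errs equally in both directions. An incidental event during the procedure would indeed be counted, but it would have to be a serious renal vascular event that merely coincided with the procedure. The documents give no reason to weight that equally.
- A reader might infer that the denominator demonstrably dilutes the rate. The default population and the reference to each time point permit a reading with little or no dilution, and the text does not settle which is meant.

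**An all-randomised denominator is legitimate, and the section promises no common basis.** Both are true: the imaging and eGFR summaries have their own denominators. The fault is that this denominator disagrees with its own lead-in and is open to more than one reading.

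**Conclusion.** The point holds in a limited form. Taken literally, the 5.7.8 wording can leave a late, procedure-caused serious renal vascular event out of the SAP 2.5.2 rate, and it is narrower than 5.7.4. The documents contain partial safeguards but no overriding rule. The number of events affected is small and cannot be determined.

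The denominator is inconsistent with its lead-in and differs from the MACE rule. If it means all randomised subjects, the rate is lower by about 0.5 to 1.2 points with 3 assumed events, 50 treated and up to 5 untreated and 5 lost, and by 2.0 points if 10 are lost. If it means Primary Analysis subjects present at the time point, the effect is nil or nearly so. Few untreated RDN subjects are likely, because randomisation follows completion of the cardiac ablation (Protocol 4.3). All these differences sit inside intervals about 14 to 19 points wide.

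This is a change that could be made, not one on which the trial's conclusions depend.

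**What to change.** 1. **Protocol 5.7.8.** Define procedure relatedness by causality: caused or possibly caused by the procedure, whatever the onset time. Reconcile the device-related wording with 5.7.4 so that the protocol has one breadth. Dual labelling is not needed for this rate, which already counts events related to either.
2. **SAP 2.5.2.** State the denominator as RDN subjects in the Primary Analysis population who had an event or were followed to the time point, matching MACE. Add the all-randomised rate or a Kaplan-Meier estimate as a supplement, because event-or-followed can overstate risk when subjects drop out.

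**Cost.** A short SAP edit, and a short protocol amendment that needs agreement, justification and ethics committee notification or approval where required (Protocol section 10). No new data collection is needed. The reported safety rate may look slightly less favourable.
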